5.3. Cost-effectiveness Analysis

We will calculate the total cost of each subject including cost of treatment, nursing, and rehabilitation from recruitment to the follow-up endpoint. The differences of total cost will be compared between the two arms using the same methods described above by treating which as a continuous variable. The total cost of intervention arm included folic

acid supplements and RBC folate examinations before conception. All the cost is settled in RMB. Further comprehensive cost-effectiveness analysis will be described by a separated SAP.

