2.1.2. Secondary objectives

The secondary objectives include to determine the effectiveness of the experimental interventions compared with the routine primary care on the following outcomes: (1) the incidence rate of fetus defects, birth defects, spontaneous pregnancy loss (including miscarriages and artificial abortions) and stillbirths related to all kinds of congenital defects; (2) the incidence of infant death or severe organ dysfunctions; and (3) prevalence of maternal gestational complications, including gestational diabetes, hypertension, and preeclampsia; (4) the medical costs related to fetus and birth defects during pregnancy and after birth.

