- Pregnant participants will receive a 75-g oral glucose tolerance test during 24-28 gestational weeks, and GDM will be diagnosed if any of the following criteria are met, based on the recommendations of the International Association of the Diabetes and Pregnancy Study Groups Consensus Panel: fasting glucose ≥ 5.1 mmol/L, 1-hour glucose ≥ 10.0 mmol/L, or 2-hour glucose ≥ 8.5 mmol/L.
- Time Frame: during 24-28 gestational weeks.
- Type: binary variable (Yes / No).

(8) Maternal gestational weight gain (kg)

- This outcome will be calculated as body weight at delivery minus weight before pregnancy (self-reported).
- Time Frame: from pre pregnancy to delivery.
- Type: continuous variable.

(9) Maternal weight gain (kg) at early gestation

- This outcome will be calculated as body weight at around 20 gestational weeks minus weight before pregnancy (self-reported).
- Time Frame: from pre pregnancy to 20 gestational weeks.
- Type: continuous variable.

(10) Occurrence of gestational hypertension

- Pregnant participants will undergo blood pressure measurements at each prenatal visit. Gestational hypertension will be diagnosed if systolic blood pressure ≥ 140 and/or diastolic blood pressure ≥ 90 mmHg, based on the recommendations of the International Society for the Study of Hypertension in Pregnancy (ISSHP).
- Time Frame: during pregnancy.
- Type: binary variable (Yes / No).

- (11) Maternal body weight (kg) at 6 months after delivery (Continuous variable)
- (12) Maternal HbA1c (%) at 6 months after delivery (Continuous variable)
- (13) Infant body weight (g) at birth, 42 day, 3 months, and 6 months (Continuous, repeated measurements)
- (14) Infant length (cm) at birth, 42 day, 3 months, and 6 months (Continuous, repeated measurements)
- (15) Infant body mass index (kg/m²) at birth, 42 day, 3 months, and 6 months (Continuous, repeated measurements)
- (16) Medical cost that relates with fetus and birth defects during pregnancy and after birth (Time Frame: from confirmation of pregnancy to one year old after birth) (Continuous variable)

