4.2. Analysis Close Date

The analysis close date will be the date on which the last participant completed follow-up to achieve the primary outcome and until age of six months.

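### The cost outcome has two definitions that differ in scope, start and end; only the one in section 5.3 takes in preconception intervention cost, and the SAP does not say which governs.

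*SAP*

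**What the plan says.** **Objective and outcome.** Section 2.1.2, objective (4), names "the medical costs related to fetus and birth defects during pregnancy and after birth". Section 2.2.2, outcome (16), agrees: "Medical cost that relates with fetus and birth defects during pregnancy and after birth", with "Time Frame: from confirmation of pregnancy to one year old after birth". It is labelled a continuous variable.

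**Analysis.** Section 5.3 states: "We will calculate the total cost of each subject including cost of treatment, nursing, and rehabilitation from recruitment to the follow-up endpoint". It then compares this total between arms as a continuous variable, using the methods already given. On intervention cost it says "The total cost of intervention arm included folic" "acid supplements and RBC folate examinations before conception". It does not mention the same items in the control arm. Only a further, comprehensive cost-effectiveness analysis is left to a separate SAP.

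**Close date.** Section 4.2 closes the analysis when the last participant has completed follow-up for the primary outcome and "until age of six months".

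**The concern.** A secondary outcome should have one scope and one time window, fixed before the data are seen. Here the outcome list and the only cost-specific analysis section describe different quantities, and nothing says which answers objective (4).

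The difference matters because the main experimental component comes before conception (section 3.3). A window that opens at confirmation of pregnancy excludes that spending. A window that opens at recruitment includes it. Left open, the choice could be made after both results are known, and the first definition would tend to show the intervention as cheaper.

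**Working it through.** The SAP gives no cost figure, standard deviation or cost-based sample size, so there is no stated number to reproduce. The check compares the texts and then works out what the difference implies.

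**Step 1. The two definitions side by side.**

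| | Objective (4) and outcome (16) | Section 5.3 |
|---|---|---|
| Scope | Medical cost related to defects | Total cost per subject (treatment, nursing, rehabilitation) |
| Start | Confirmation of pregnancy | Recruitment |
| End | One year after birth | Follow-up endpoint, not defined |
| Preconception folic acid and RBC tests | Outside the window | Included for the intervention arm; controls not mentioned |

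They differ on every row. The table shells in section 7 have no cost row, so they do not settle the matter.

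**Step 2. The close date.** Under 4.2 the last infant need only reach six months. Any infant born less than a year before the close date would then have an incomplete one-year window for outcome (16). This holds whatever the follow-up endpoint in 5.3 is meant to be.

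**Step 3. Effect on the arm difference.** Inputs:
- Event proportions of 8% (control) and 4% (experimental), from section 3.5.
- C, the cost per affected case. Not in the SAP; assumed 2,000 to 50,000 RMB.
- I, the extra preconception cost per experimental woman. Not in the SAP; assumed 100 to 1,000 RMB.

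Assume equal cost per case in both arms and equal other costs. Experimental minus control, per woman:
- Outcome (16): (0.04 − 0.08) × C = −0.04C.
- Section 5.3: −0.04C + I.

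The definitions differ by I. The signs are opposite only if I > 0.04C, that is, I > C/25.

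| Assumed C (RMB) | Break-even I = 0.04C | Assumed I | Outcome (16) | Section 5.3 |
|---|---|---|---|---|
| 2,000 | 80 | 100 | −80 | +20 |
| 5,000 | 200 | 300 | −200 | +100 |
| 10,000 | 400 | 500 | −400 | +100 |
| 20,000 | 800 | 500 | −800 | −300 |
| 50,000 | 2,000 | 100 to 1,000 | −2,000 | −1,900 to −1,000 |

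The first three rows reverse and the last two do not. In every row the estimate moves by I.

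**Step 4. Cost items.** Section 5.3 names folic acid and RBC tests only. The experimental package in 3.3 also has nurse calls, advice based on MTHFR genotype, and referral after delivery; 5.3 does not say whether these are costed. RBC folate is also measured in controls: the per-protocol rule in 4.1 needs a first-visit value in both groups. Section 5.3 does not say whether control tests count as cost or as research activity.

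**The case against.** The best defence is that these are two quantities, not one quantity defined twice. Outcome (16) is continuous, so 5.2.2 already supplies its analysis. Section 5.3 has a cost-effectiveness heading, names total cost and points to a later SAP. That reading is possible, but the document never states it. Section 5.3 is the only section that addresses cost specifically, and only the further comprehensive analysis is deferred. If two endpoints are meant, they need labels and one must be named as the secondary outcome.

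Other objections limit the point, and they stand:
- Charging an intervention to the arm that receives it is normal costing, not bias.
- A reader might infer that folic acid bought by control women is excluded. Section 5.3 is silent on controls; it neither excludes their costs nor says its list is complete.
- A reader might take six months as the follow-up endpoint. Section 4.2 sets the analysis close date and does not define that term.
- A reader might count all expert referral as experimental cost. The text of 3.3 gives the antenatal green channel and expert consultation to both arms, although its table lists antenatal consulting under the experimental arm. Only referral after delivery is clearly additional.
- The break-even is a simplification. Added referral could change cost per case, total cost need not be equal apart from defects, and the 28-day composite stands in for cases that generate cost up to one year.

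**Conclusion.** The inconsistency is real. The outcome list and section 5.3 give different scope, start and end for cost, and no passage ranks or separates them. The one-year window also runs past the point at which 4.2 can close the analysis.

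Under equal cost per case and equal other costs, the gap between the two arm differences is the extra preconception cost per experimental woman. It is tempting to conclude that the choice of passage reverses the cost result. The SAP does not support that: reversal requires a preconception cost above 0.04 times the cost per affected case, and no unit costs are given. What is established is that the two rules yield different estimates.

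This affects one secondary outcome and not the primary conclusion. It should still be corrected, because the change is small and the open choice bears directly on the reported cost difference.

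**What to change.** 1. In 2.2.2(16) and 5.3, either state one cost outcome with one scope, start and end, or label two endpoints (defect-related cost, and total cost including the intervention) and say which is the secondary outcome.
2. Define the follow-up endpoint, and reconcile it and the one-year window with 4.2.
3. Give one cost-item list and apply it by the same rule in both arms. Count folic acid wherever it is used, and state how control-arm RBC tests are treated.
4. State whether nurse calls, genotyping and post-delivery referral are costed.

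This is mainly a change of SAP wording. It brings some extra costing work, and the total-cost result may be less favourable to the intervention.

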3.3. Interventions

Experimental interventions: usual care plus additional procedures

- Before conception:

Participants will be examined for serum and RBC folate concentrations at enrollment to identify those with insufficient RBC folate concentration (<400ng/mL). Based on reviewing of folate supplement status of from the participant-administered questionnaire, a trained nurse will call the participant to inform them the RBC folate concentration and folate metabolism ability evaluated by one's genotypes of MTHFR C677T variant, and provide individualized folic acid supplementary instructions to improve folate status before get pregnant. A second RBC folate test is booked.

- During gestation -- Green channels for confirmation of fetus defects and a following genetic and clinical consulting:

In the both arms, fetus and infants with screen positive of fetus defect(s) will be referred via a green channel to approach an authorized tertiary obstetric hospital to achieve timely further routine comprehensive assessments and confirmative diagnosis. Then the participants with established diagnosis of fetus defects will be referred to a multi-discipline paediatric expert team for a deep consultation about possible postnatal treatments in the future to avoid unnecessary abortions.

- **After delivery:**

The participants from the experimental arm will additionally provide timely referral to a prespecified team of pediatrician experts for timely medical treatment or scheduled follow-up.

Standard tertiary interventions of birth defects (control arm, usual care):

Couples eligible for reproductive policy are entitled to routine health cares including general health cares (health education, medical history inquiry, physical examinations, consulting guidance and pregnancy outcome follow-up) and medical examinations (laboratory examinations, virus screenings and image examinations). But nutrients status is not included in these examinations, such as folate, vitamin B12 and microelements, etc. Regular antenatal cares are required, such as deformity screening by ultrasound. Routine neonatal screenings are conducted to diagnose infant with birth defect(s) timely.

Intervention procedures of FOID study

	Experimental arm Procedures in addition to the usual care	Control arm Usual care
Before conception		
Preconception at enrollment	RBC folate test Inform and instruction about folic acid supplementation via phone interview	Routine physical examination and routine blood tests

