4. ANALYSIS POPULATIONS

4.1. Study Population Data Sets

Two study populations will be considered in the analysis as follows:

- **Intent-to-Treat (ITT) population**

ITT population will be defined as the pregnant women among preparing-for-pregnancy couples that were recruited since November 1, 2018, from the randomized clusters and finally get pregnant. Participants will be excluded from the ITT analysis if the primary outcome is missing, forming a modified ITT population (mITT).

- **Per protocol (PP) population**

PP population will only include participants who received the treatments according to the protocol. Specifically,

- Participants of the experimental group: will be considered non-compliant with the preconception intervention if their RBC folate levels do not reach the target level (400 ng/ml) at the 1st antenatal visit.
- Participants in the control group received the usual care only, no non-complaints will be defined.
- Participants in both groups who do not have RBC folate levels measured at the 1st antenatal visit will not be included in the PP population.

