5.2. Secondary Outcome Analysis

All secondary outcomes will be analysed as a superiority design and two-sided 95% CIs for the treatment differences in these outcomes between the two arms will be calculated and presented. Secondary outcome analyses will be based on the ITT population unless specified.

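### Section 5.3 counts cost from recruitment, but every analysis set is limited to women who conceived, so the experimental arm's preconception cost per pregnancy is understated

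*SAP*

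**What the plan says.** **Cost window and items (SAP 5.3).** The plan states: "We will calculate the total cost of each subject including cost of treatment, nursing, and rehabilitation from recruitment to the follow-up endpoint". The intervention arm's total includes folic "acid supplements and RBC folate examinations before conception". On method: "The differences of total cost will be compared between the two arms using the same methods described above by treating which as a continuous variable". Section 5.3 names no analysis population, and leaves a fuller cost-effectiveness analysis to a separate SAP.

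**Populations (SAP 4.1).** "Two study populations will be considered in the analysis as follows": ITT and PP. For the first, "ITT population will be defined as the pregnant women among preparing-for-pregnancy couples", namely those "recruited since November 1, 2018, from the randomized clusters and finally get pregnant". A modified ITT set then drops women whose primary outcome is missing. PP requires an RBC folate value at the first antenatal visit.

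**Default (SAP 5.2).** "Secondary outcome analyses will be based on the ITT population unless specified". Medical cost is secondary outcome 16 in section 2.2.2.

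**Timing of the spending (SAP 3.3, experimental arm).** "Participants will be examined for serum and RBC folate concentrations at enrollment to identify those with insufficient RBC folate concentration". A nurse call, supplementation instructions and a booked second test follow, all before conception.

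**The concern.** Testing and supplementation are paid for at and after enrolment, before anyone knows which women will conceive. A programme that offers them to all women planning pregnancy bears that cost for every woman, including those who never become pregnant. Section 5.3 means to capture it, since it starts the count at recruitment and names the items. The only populations available for the comparison, however, leave out the women on whom part of the money was spent.

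What is at stake is the reported cost of the intervention per pregnancy. If the plan is followed as written, each experimental-arm pregnancy carries only its own preconception cost and no share of the cost of the enrolled women who did not conceive.

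**Working it through.** The SAP gives no unit cost, conception rate or expected cost difference, so there is no plan figure to reproduce. The check is one of definitions, followed by algebra.

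**Step 1. Can any defined set hold a woman who never conceived?**
- ITT: no, pregnancy is part of the definition.
- Modified ITT: no, it is a subset of ITT.
- PP: no, a first antenatal visit is needed.

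Her preconception cost therefore enters no comparison.

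**Step 2. Notation (experimental arm).**
- N: women enrolled.
- q: share who conceive. Not in the SAP; assumed 0.5 to 0.9.
- c_C and c_N: mean preconception intervention cost per woman who does and does not conceive. Not in the SAP.
- D: difference between arms (experimental minus control) in later cost per pregnancy. Not in the SAP.

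**Step 3. Preconception cost per pregnancy.**
- Spent: N[q·c_C + (1 - q)·c_N]. Over Nq pregnancies: c_C + c_N(1 - q)/q.
- Counted under the plan: c_C.
- Shortfall: c_N(1 - q)/q, which cannot be negative. If both groups cost the same, c_C = c_N = c, it is c(1/q - 1).

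| assumed q | share of preconception spending omitted (1 - q) | actual cost per pregnancy (c/q) | shortfall |
|---|---|---|---|
| 0.9 | 10% | 1.11c | 0.11c |
| 0.7 | 30% | 1.43c | 0.43c |
| 0.5 | 50% | 2.00c | 1.00c |

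The 10% in section 3.5 is a dropout allowance. The SAP does not say that it covers non-conception, so it does not fix q at 0.9.

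**Step 4. Does the direction hold on other scales?** Take equal c, and no preconception cost charged to controls.
- Planned comparison (women who conceived only): c + D.
- Per pregnancy, all spending counted: c/q + D, never below the planned figure.
- Mean per enrolled woman, with the same q in both arms: c + qD. Planned minus this is D(1 - q), so the sign is that of D.

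With c = 1 and q = 0.7:

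| D | planned | per enrolled woman | per pregnancy, all spending |
|---|---|---|---|
| -0.5 | 0.50 | 0.65 | 1/0.7 - 0.5 = 0.93 |
| +0.5 | 1.50 | 1.35 | 1/0.7 + 0.5 = 1.93 |

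The per-pregnancy understatement is the same in both rows (0.43). Per enrolled woman, the planned figure is too low in the first row and too high in the second.

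**Step 5. The other cost definition.** Secondary outcome 16 (section 2.2.2) covers only costs related to defects and starts when pregnancy is confirmed. Section 5.3 covers total cost and starts at recruitment. Under the first window, a set of pregnant women is coherent and preconception cost is out of scope. Under the second, it is not coherent.

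**The case against.** **A reader might infer that the omission always makes the intervention look cheaper.** The documents do not support that. Per enrolled woman the direction follows the sign of D. The planned halving of defects (8% to 4%, section 3.5) suggests D below zero, but section 3.3 also gives the experimental arm specialist consultation, neonatal heart screening with echocardiography, and referral, so D above zero cannot be excluded.

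**A reader might also infer that controls have no matching cost.** This is not settled. Section 3.1 describes blood sampling for RBC folate at enrolment without limiting it to one arm, section 5.1.2 uses baseline RBC folate as a covariate, and Table 2 in section 7 reports it for both arms. Section 3.3 points the other way, because usual care does not examine folate status. Whether control tests are costed is not stated. If they are, the same omission occurs there and partly offsets the error in the difference between arms. Exclusion for a missing primary outcome likewise removes costs from both arms.

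**ITT is inferred for section 5.3.** It names no population, and its reference back to earlier methods may mean only the model. This is true, but cost is a listed secondary outcome and no wider set exists. If section 5.3 means every recruited woman, the SAP defines no set to match, and the population still has to be stated.

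**A separate SAP will follow.** Section 5.3 defers only the further analysis; the comparison of total cost between arms is fixed here. What the separate SAP will do is unknown, so nothing can be said about carry-over into a later cost-effectiveness ratio.

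**The size is conditional.** This stands. The factor 1/q scales only the preconception component, not total cost, and the nurse call is not among the items that section 5.3 names.

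**Conclusion.** The point holds in this limited form. The recruitment-based cost window and the pregnancy-based populations do not fit together, and preconception spending on experimental-arm women who do not conceive is left out. That arm's total cost and its cost per pregnancy are then understated with certainty whenever some enrolled women do not conceive and money was spent on them. The per-pregnancy shortfall is c(1/q - 1), or 0.11c, 0.43c and 1.00c at assumed q of 0.9, 0.7 and 0.5. The size rests on equal mean spending for women who do and do not conceive; the direction does not.

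For the difference between arms per pregnancy, the direction also requires that any costed control-arm tests leave a smaller shortfall than the experimental arm's. No direction can be claimed for mean cost per enrolled woman. This concerns a secondary analysis and leaves the primary outcome untouched. It should be corrected before the cost comparison is run.

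**What to change.** 1. In section 5.3, name the population. Keep the pregnancy as the unit, but charge each analysed pregnancy its arm's total preconception intervention cost over all enrolled women divided by the number of analysed pregnancies in that arm. Apply the same rule to any control-arm tests that are costed, and say whether they are.
2. Optionally, add mean cost per enrolled woman as a separate estimand, labelled as such because it answers a different question. It needs a stated end of follow-up for women who do not conceive; section 4.2 ties closure to the primary outcome and the age of six months.
3. Reconcile section 5.3 with secondary outcome 16 on both the start of the window and the scope (total or defect-related cost).

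**Cost.** A few sentences of SAP text and some extra analysis work. Appendix 2.1 already lists recruitment date, community, and first and repeat test dates, so tests can be counted for all recruited women. Appendix 2 lists no cost variable and no quantity of supplements, so supplement cost may need a standard unit cost. The reported cost per pregnancy will be less favourable to the intervention.

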6. GENERAL CONSIDERATIONS FOR DATA ANALYSES

STATA® (version 15.0) will be used to perform all data analyses and generate the majority of data displays. SAS or SPSS or S-Plus or R may also be used for some data analyses and generating statistical graphs.

